Laboratory Tests – Urine and blood samples will be collected and sent to a central laboratory for analysis (see [Section 6.3](#) for details).

Pregnancy Test – All female subjects of childbearing potential will have a serum pregnancy test performed at Screening and a urine pregnancy test at Randomization and Follow-up. Childbearing potential will be defined as any female subject who has not undergone surgical sterilization within the last 3 months or who is not post-menopausal for at least 1 year.

Adverse Events – AEs will be reported by the subject from the time of informed consent through the end of the follow-up period. AEs will be followed by the Investigator as determined by Sponsor or designee. Further details on AE reporting are provided in [Section 7](#).

Concomitant Therapy – A complete history of medications (prescribed and over-the-counter [OTC]) used within the past 30 days will be recorded, including herbal remedies and contraceptives. A full history of constipation medication use should be collected, with particular focus on any constipation medications taken within the 90 days prior to screening. The subject must be instructed to stop all disallowed prescription and laxative medications per [Section 5.7.1](#) of the protocol. A subject who has been routinely administering a daily fiber supplement and/or concomitant blood pressure lowering medication for at least 30 days preceding the Screening Visit may remain on the supplement/medication throughout the study provided the regimen and dose does not change.

Drug Accountability – All study medication received at the site will be inventoried and accounted for throughout the study and the result recorded in the Drug Accountability Form and in subject's eCRF. Study medication supplies for each subject will be inventoried and accounted for throughout the study. Study medication administration will be documented in the source documentation, including dispensation information and capsule counts, and entered in the appropriate eCRF page.

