8.2 Datasets Analysed

Four analysis populations, the modified Intent-to-Treat (mITT) population, the Per Protocol (PP) population, the Completers population, and the Safety population, will be defined as follows:

- **The mITT population** will include all randomized subjects who take at least one dose of study medication and have at least one diary entry. This dataset will be used for summarization of demographic and baseline characteristic data, and for all efficacy analyses.
- **The PP population** will consist of all mITT subjects who met all eligibility (i.e., inclusion/exclusion) criteria at study entry, did not have any major protocol violations, had an overall diary compliance of at least 70%, and had a dosing compliance within 75% to 125%. Dosing compliance will be verified by the use of diary data. Supportive efficacy analyses will be performed on this population to evaluate the impact of major protocol violations.
- **The Completers population** will consist of only those subjects who complete the entire treatment period of the study with a recorded primary endpoint and will be used for supportive efficacy analyses.

- **The Safety population** will consist of all randomized subjects who take at least one dose of double-blinded study medication. Analyses on the Safety population will be based on the actual treatment received.

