8.4 Analysis of Exposure to Study Medication, Rescue Medication, and Concomitant Medication

8.4.1 Analysis of Study Drug Exposure and Compliance

Exposure to study medication and study drug compliance will be summarized by treatment group and overall using descriptive statistics. The exposure to study medication is defined as the last dose date of study medication minus the first dose date of study medication plus 1 day. Percent compliance will be calculated as the total number of daily dose divided by the total number of expected doses. The total number of expected doses will be calculated as the total number of study medication exposure (day) times 2.

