SBM frequency rate at week 1 will be summarized by treatment group. The 90% CIs of the treatment ratio between the sprinkle and capsule formulations will be calculated. ANCOVA, using Week 1 SBM frequency rate as the dependent variable will be used to compare treatment groups with baseline SBM frequency rate as a covariate. The van Elteren test stratified baseline SBM frequency rate (< 1.5 or ≥ 1.5) and pooled sites will be performed to detect differences from baseline for lubiprostone sprinkle and lubiprostone capsule vs. matching placebo.

In order to adjust for early withdrawals or missing days, subjects with less than 7 days of treatment will have the Week 1 SBM frequency rates adjusted as follows:

$$7 \times \text{Number of SBMs} / (\text{Number of days treated}).$$

If the number of observed days is less than 4 days, then the data will be considered insufficient and the rate will be missing for that subject. No imputation will be performed for missing data.

8.5.3.5 Mean Change from Baseline in SBM Frequency Rate at Week 1

Changes from baseline in SBM frequency rate at week 1 will be summarized by treatment group. The 90% CIs of the treatment ratio between the sprinkle and capsule formulations will be calculated. ANCOVA for the change from baseline in observed SBM count and the van Elteren test stratified by baseline SBM frequency rate (< 1.5 or ≥ 1.5) and pooled sites will be performed for the following comparisons:

- The sprinkle formulation of lubiprostone vs. the placebo group
- The capsule formulation of lubiprostone vs. the placebo group

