APPENDIX 3 SUBJECT BOWEL HABITS DIARY

The electronic diary will be completed each evening by the subject. The diary will be set up so that it may be completed each evening with responses based upon the last day.

Item/Instruction Text	Response Options
INSTRUCTIONS DAILY ASSESSMENTS The following questions will be assessed as part of the subject's daily diary. Subject will record their answers to these assessments for the entire duration of the study. Diaries are to be completed from the beginning of the screening period through the end of the double-blinded treatment period. Please note that the questions may be asked in an order different from what is presented below.	
STUDY MEDICATION Did you take your Morning Dose of STUDY MEDICATION today?	Yes No
What time did you take the Morning of STUDY MEDICATION Dose?	Morning Dose – xx:xx AM
STUDY MEDICATION Did you take your Evening Dose of STUDY MEDICATION today?	Yes No, not yet No, not taking tonight
What time did you take the Evening Dose of STUDY MEDICATION today?	Evening Dose – xx:xx PM
RESCUE MEDICATION Over the last day: Did you take a RESCUE MEDICATION to help you have a bowel movement?	Yes No
[If YES] Please indicate the OTHER RESCUE MEDICATION you used?	Bisacodyl Saline enema Other
[X will be equal to the other medicine selected in prior item response.] Did you take this RESCUE MEDICATION today or yesterday?	Today Yesterday

X	[spinner xx:xx]																					
Please record the time of this dose of RESCUE MEDICATION.																						
BOWEL MOVEMENTS Confirm you would like to report a Bowel Movement you had today or yesterday: Today's Date: DD MON YYYY Yesterday's Date: DD MON YYYY	Yes No																					
Did this bowel movement occur today or yesterday? - Will be asked for each bowel movement	Today Yesterday																					
Please record the time of this bowel movement. - Will be asked for each bowel movement	[spinner xx:xx]																					

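### The Week 1 SBM frequency rate is corrected by treatment days, so missing diary days in fully dosed subjects go uncorrected; the change-in-rate ANCOVA also names the wrong variable

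*Combined protocol and SAP*

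**What the plan says.** Section 8.5.3.4 opens its correction with "In order to adjust for early withdrawals or missing days, subjects with less than 7 days of treatment", which gives both the purpose and the trigger. The corrected rate is 7 times the number of SBMs divided by "Number of days treated". The next sentence changes the unit: "If the number of observed days is less than 4 days, then the data will be considered insufficient", and the rate is then missing. The section closes by ruling out imputation, and Section 8.5.1.1 limits missing-data adjustment to the observed SBM count.

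Section 8.5.3.4 does not define the divisor. The nearest definition is exposure in Section 8.4.1, the "last dose date of study medication minus the first dose date of study medication plus 1 day". Section 8.5.3.4 does not refer to it, and it does not depend on diary completion.

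Section 8.5.3.5 covers change from baseline in the SBM frequency rate, a secondary endpoint listed in Section 2.2.1.2. Its heading, summary and ratio confidence interval concern the rate. Its ANCOVA is specified for change in observed SBM count, in the same words as Section 8.5.3.2, and no covariate is named.

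**The concern.** The rule has two stated purposes, and its wording serves only one. For a subject who stops treatment early, dividing by days treated rescales the count to a week. For a subject who takes study medication all week but leaves diary days blank, the trigger never fires, and the partial count stands as a full-week rate. The four-day minimum shows that the plan expects to use subjects with 4, 5 or 6 observed days.

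At stake are a rate biased downwards for those subjects, and two statisticians deriving different values from one diary because one divides by days treated and the other by days observed. In Section 8.5.3.5, the text as written specifies no ANCOVA for a listed endpoint and specifies the count ANCOVA twice.

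**Working it through.** The plan states no figure for this rule, so there is none to reproduce. The check compares the literal rule with an observed-day divisor.

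**Inputs.** The Week 1 mean SBM count on lubiprostone capsules is 5.62 with SD 4.24, and 156 subjects per group are required (Section 8.1). The 5.62 is a historical observed count. Using it as a complete-week mean is an assumption made for illustration, since it may already include missing days. SBMs are taken as spread evenly over the week. A lost day is one whose bowel movements never reach the diary.

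**Single subjects.**
- Dosed 7 days, 5 observed, 4 SBMs: the literal rule gives 4.00; the observed-day rule gives 7 × 4 / 5 = 5.60.
- Withdrawn after 4 days, all 4 observed, 3 SBMs: both rules give 7 × 3 / 4 = 5.25.

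The two rules agree when days treated equal days observed and part when they do not.

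**Expected size, dosed all 7 days, m days lost.** Literal rate = 5.62 × (7 − m)/7, a shortfall of m/7.
- m = 1: 5.62 × 6/7 = 4.82, low by 14.3%.
- m = 2: 5.62 × 5/7 = 4.01, low by 28.6%.

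The observed-day rule returns 5.62 in both cases. These are expectations. In an assumed gamma-Poisson model with the mean and SD above, about half of subjects (49.7%) lose no SBM when one day is lost.

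**Arm level.** The share s with a lost day is not in the documents. Assume one lost day each and s from 5% to 30%. Arm mean = 5.62 × (1 − s/7), which is 5.58 at 5% and 5.38 at 30%, a fall of 0.7% to 4.3%. With the same s in every arm, differences from placebo shrink by the same proportion.

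**Placebo tests.** The SD falls with the mean, so the test statistic moves less. In the same model, with 156 per arm, a common coefficient of variation and s = 30% in both arms, it falls from 6.80 to 6.71 for an assumed placebo mean of 3, and from 3.88 to 3.83 for a mean of 4. Each is a fall of about 1.3%.

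**Sprinkle/capsule ratio.** Equal missingness cancels. With an assumed 10% affected in one arm and 20% in the other, (1 − 0.2/7)/(1 − 0.1/7) = 0.986, a shift of 1.4%.

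**Section 8.5.3.5.** No arithmetic applies to the variable name. On the covariate, an ANCOVA of the rate and one of change in rate give the same treatment difference and p-value when both include baseline rate. The ANCOVA in Section 8.5.3.4, which has that covariate, therefore already supplies the intended comparison.

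**The case against.** The best defence is that days treated is loose wording for observed treatment days. Purpose, formula and minimum stand in one short paragraph, and read together they could mean a single day count. That is plausible, and under it the rule works. But the paragraph uses two different terms, its trigger is expressed as treatment, and the only nearby definition is a dose-date span. The separate SAP announced in Section 8 may settle the matter; it is not among the documents.

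The Per Protocol diary rule also limits the problem. If its 70% threshold were applied to the treatment week, 5 of 7 evenings (71.4%) would pass, so at most two could be missed. Section 8.2 says only that compliance is overall, and the mITT population, also used for efficacy, needs a single diary entry.

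Stronger readings are tempting, but the documents do not support them:
- A reader might infer that the divisor counts days with a diary dose record, because "Dosing compliance will be verified by the use of diary data". The dose items ask about the current day ("Did you take your Evening Dose of STUDY MEDICATION today"), while movements can be dated a day back ("Confirm you would like to report a Bowel Movement you had today or yesterday"), so a missed evening would inflate the rate. But that sentence concerns Per Protocol membership and is not tied to the rate. Nor does a missed evening always remove the dose record: the Day 1 dose time is entered in the diary in clinic (Section 6.1.2.2).
- A reader might infer that a missed Day 7 evening is handled differently by diary and eCRF dose dates. Section 6.1.1 says "Study medication administration will be documented in the source documentation, including dispensation information and capsule counts, and entered in the appropriate eCRF page", but it does not say that a last-dose date is captured independently of the diary.
- A reader might extend the shortfall to three lost days. If previous-day entries recover what they can, three days lost mid-week need four missed evenings. That leaves three entries, and if observed days means evening entries, the rate is then missing.

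The objection that Section 8.5.3.5 contains only a wording slip is fair: the endpoint is clear from its heading and from Section 2.2.1.2.

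**Conclusion.** The point holds as a minor correction to two secondary endpoints. Taken literally, Section 8.5.3.4 does not adjust for missing diary days in fully dosed subjects, although it says that it adjusts for missing days. The expected shortfall is m/7 per affected subject, given evenly spread SBMs and no recovery of the lost days. The share affected is unknown. Over the assumed range, arm means fall by a few per cent at most and placebo tests barely move.

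A reader might infer that the equivalence conclusion is at risk. It is not: the primary analysis uses the LDOCF count, and neither the sample size nor the [0.8, 1.25] criterion depends on this rate. The ANCOVA variable in Section 8.5.3.5 is wrong as written but costs little, because Section 8.5.3.4 already has a baseline-adjusted ANCOVA of the rate.

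**What to change.** In Section 8.5.3.4, use observed days for the trigger, the divisor and the four-day minimum. For any subject with fewer than 7 observed days, rate = 7 × (SBMs dated to observed days) / (number of observed days). Define an observed day as a treatment day whose own evening diary entry was completed. This rests on unobserved days resembling observed ones. The small downside is that movements entered later for a day without its own entry are not counted in the rate. Including such days would not be safer: the diary records a previous-day movement only if the subject chooses to report one, so silence cannot be told from zero.

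In Section 8.5.3.5, make the ANCOVA dependent variable change in SBM frequency rate, with baseline SBM frequency rate as covariate, as in Section 8.5.3.4.

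Carry both changes into the SAP before unblinding; if the SAP already defines days treated, align the two texts. The cost is one definition and a few words, with no new data.

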8.5.4 Sensitivity Analysis of Primary Efficacy Endpoint

The primary analysis will be performed for the following specific population to assess the robustness of the primary analysis:

PP subjects discontinued early due to lack of efficacy after completing 3 days of treatment and PP subjects discontinued early because of taking the rescue medication during the 1-week treatment period will be included. PP subjects discontinued early for other reasons are excluded.

8.5.5 Subgroup Analysis

The primary efficacy analysis will also be performed in demographic subgroups including age, gender, and race to assess the consistency of treatment effect. Additional subgroup analyses based on other baseline characteristics and stratification factors may also be conducted.

8.6 Analysis of Safety

8.6.1 Deaths, Serious Adverse Events, and Discontinuations Due to Adverse Events

Subjects with these critical events will be identified in separate listings, with the event, timing and outcome information and relevant demographic and baseline data.

8.6.2 Adverse Events

The original terms used in the eCRF by Investigators to identify AEs will be coded to MedDRA® system organ class and preferred terms. Adverse events will be summarized in terms of incidence per dose group and overall. The incidence of an AE is defined as the number of subjects who experienced at least one episode during the study. Adverse event incidence rates will be summarized by system organ class (SOC) and preferred term (as determined by the coding).

Whatever the level of classification, if a subject experiences multiple episodes of an event within the given time reference, then the event is only counted once. Further, for summaries by severity or causality, the most severe event is chosen for a subject if that subject experiences multiple episodes of the same event

AEs with onset dates between consent and prior to administration of the first dose of study medication or after the last day of treatment + 7 days will be considered non-treatment emergent, and excluded from the tabulations. Events with completely or partially missing onset dates will be included in the tabulations unless the available partial date information clearly indicates that the event happened outside of the treatment period.

P-values from Fisher's exact test or chi-square test will be presented in the AE summary tables. The test will be performed to compare incidence rates between the sprinkle and capsule formulations of lubiprostone and the matching placebo group.

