3.1 Study Procedure Overview

A detailed description of the procedures to be performed is outlined in [Section 6](#). The schedule of events is outlined in tabular format in the Protocol Synopsis section.

There will be four distinct visits for the study:

- **Screening Period (Visit 1; Day -14 [-3 days]):** This visit will occur up to 17 days prior to the first dose of study medication to determine subject's eligibility for participation in the study. This period includes a diary eligibility period during which subjects will record their bowel habits data prior to randomization.
- **Randomization Visit (Visit 2; Day 1):** This visit is considered Day 1, occurring after the subject has completed the screening requirements and taking place on the first day of study medication administration.
- **End-of-Treatment Visit (Visit 3; Day 8 [+2 days]):** Clinical and laboratory assessments will be performed to evaluate the safety of study treatment. This is the final visit of the treatment period and should be conducted for all subjects including subjects who discontinue early from the study.
- **Follow-up Visit (Visit 4; Day 15 [+3 days]):** A follow-up clinic visit will occur to perform post-treatment clinical and laboratory assessments. This will conclude the subject's involvement in the study.

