6.1.4 Follow-up Period

The Follow-up period lasts until Day 15 (+3 days). AEs should be followed to assess their status and resolution during this timeframe. Any new concomitant medications should also be recorded.

At this visit the following procedures will be performed:

- Measure vital signs, including weight. Subjects should be asked to remain supine for at least 5 minutes prior to measurement of vital sign parameters;
- Perform an abbreviated physical examination;
- Collect blood and urine samples for laboratory analysis;
- Review and update concomitant therapy; and
- Review and record any new AEs.

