7. ADVERSE AND SERIOUS ADVERSE EVENTS

As defined in ICH GCP Guideline E6,⁷ an AE is any untoward medical occurrence in a clinical investigation subject administered a pharmaceutical product and which does not necessarily have a causal relationship with this treatment. An AE can therefore be any unfavorable and unintended sign (including an abnormal laboratory finding), symptom, disease or exacerbation of a pre-existing condition temporally associated with the use of a medicinal (investigational) product, whether or not related to the medicinal product. For this study, all safety information will be collected from the time of informed consent and any untoward medical occurrence after screening will be defined as an AE. Adverse events that are reported after initiation of study medication, and on or before the last day of study medication plus 7 days, will be defined as treatment-emergent AEs.

Each AE requires a complete and thorough description including date of onset, duration, intensity/severity, its relationship to the study drug and any corrective actions taken. Each AE should also be categorized as “serious” or “non-serious”.

Timely, accurate, and complete reporting and analysis of safety information from the clinical study are crucial for the protection of subjects and are mandated by regulatory agencies worldwide.

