7.1.5 Onset and Duration

The date and time the event was reported to investigator will be recorded, as well as the start date and time and resolution date and time of the event.

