7.2 Recording and Reporting of Adverse Events

All AEs will be recorded in the source document and applicable eCRF(s) from the time the informed consent is signed until the end of study. AEs occurring prior to the first dose of study drug will be considered non-treatment emergent. The Investigator shall notify the Sponsor at any time when an SAE is believed to be related to the administration of study medication, even after the end of the study. At any time during the study, those events meeting the definition of an Immediately Reportable Event (IRE) must be recorded on source document, IRE Reporting Form, and applicable eCRF(s), and then reported to Sponsor or designee using the IRE Reporting Form as specified in [Section 7.2.1](#).

All AEs, regardless of seriousness, severity or presumed relationship to study medication, must be recorded using medical terminology in the source document and in the eCRF. Whenever possible, diagnoses should be given when signs and symptoms are due to a common etiology (e.g., cough, runny nose, sneezing, sore throat, and head congestion should be reported as “upper respiratory infection”). Investigators must record on the source document and eCRF their opinion concerning the relationship of the AE to study therapy and the severity of the event. All measures required for AE management must be recorded in the source document and reported according to Sponsor instructions.

For any subject who is discontinued from the study due to an AE, it is expected that the Investigator will follow the subject until the event resolves, the event returns to baseline (if a baseline value is available), or until such time that the Investigator does not anticipate any further improvement or worsening of the event.

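### Section 8.6.2 has no rule for a screening AE that worsens on treatment, so its place in the AE tables depends on how the site records it; section 7 also words treatment-emergence by report date

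*Combined protocol and SAP*

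**What the plan says.** **Tabulation rule.** Section 8.6.2 treats as non-treatment-emergent, and leaves out of the tables, "AEs with onset dates between consent and prior to administration of the first dose of study medication", together with AEs that start more than 7 days after the last treatment day. Its rule for missing dates also works on onset. It does not mention an event that starts before dosing and worsens afterwards. The tables carry p-values comparing the lubiprostone formulations with placebo.

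**Other statements of the definition.** Section 7.2 says "AEs occurring prior to the first dose of study drug will be considered non-treatment emergent", and footnote 8 of the Schedule of Evaluations says the same in substance. The opening paragraph of section 7 differs. It defines as treatment-emergent "Adverse events that are reported after initiation of study medication, and on or before the last day of study medication plus 7 days".

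**Recording.** The AE definition in section 7 includes a "symptom, disease or exacerbation of a pre-existing condition temporally associated with the use of a medicinal (investigational) product". Section 7.1.5 keeps two dates apart: "The date and time the event was reported to investigator will be recorded, as well as the start date and time". AEs are collected from consent. At the Randomization and End-of-Treatment visits (sections 6.1.2.2 and 6.1.3.1) sites record new AEs and follow those still open. At the follow-up visit (section 6.1.4) they are to "Review and record any new AEs".

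**The concern.** Screening lasts 14 to 17 days, and AEs recorded in it carry a pre-dose onset. If such an event is still open on Day 1 and becomes more severe on drug, that increase is on-treatment safety information. Under section 8.6.2 as written, the record's onset date decides whether it is tabulated. A site that updates the severity on the existing record removes the event from both the incidence and the severity tables. A site that opens a new record keeps it in. With about 70 sites, the same clinical course can be counted differently from site to site.

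AE incidence is a named safety endpoint (section 2.2.2) and is tested against placebo. The comparison would be biased only if more drug-attributable worsening were lost on lubiprostone than on placebo. The bias would then be toward no difference.

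The report-date wording in section 7 is a secondary matter. Report date and start date are both captured, so either rule could be programmed, and the two can classify the same event differently.

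**Working it through.** The plan states no figure to reproduce. The check applies each rule to the same cases and then works out the visit days.

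**Cases**

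| Case | Section 8.6.2 (onset) | Section 7 opening (report) |
|---|---|---|
| A. Screening AE, worsens on drug, kept on its existing record | Excluded | Not treatment-emergent (reported before dosing) |
| B. Same course, worsening entered as a new AE with post-dose onset | Counted | Treatment-emergent if reported inside the window |
| C. Pre-dose onset, first reported after dosing, inside the window | Excluded | Treatment-emergent |
| D. Onset on Day 11, first reported at Visit 4 after the window has closed | Counted | Not treatment-emergent |
| E. Onset after the window | Excluded | Not treatment-emergent |

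A and B are the same clinical course, and only the site's record-keeping separates them. Section 7.2 and footnote 8 do not help with A, because they too go by occurrence before first dose. C and D are where the report-date and onset rules disagree.

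**Is a new entry required in case A?** Section 7 makes an exacerbation eligible to be an AE. Section 7.2 requires all AEs to be recorded. Neither says that the worsening of an AE already on file gets its own record or a new onset date. Sections 6.3, 7.2.3, 7.2.4 and 7.2.5 deal with examination changes, constipation symptoms, laboratory values and vital signs. None of them sets a re-dating or treatment-emergence rule.

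**Visit days for case D**

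Inputs:
- Last dose on the evening of Day 7 (sections 3 and 6.1.2.2), or on the evening before Visit 3 (section 5.5 and Schedule footnote 9).
- Visit 3 on Day 8 to 10.
- Follow-up: "The Follow-up period lasts until Day 15 (+3 days"), that is, Visit 4 on Day 15 to 18.

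Formula: window closes on last dose day + 7.

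- Last dose Day 7: 7 + 7 = Day 14. Visit 4 falls 15 − 14 = 1 to 18 − 14 = 4 days after closing.
- Last dose Day 8 (evening before a Day 9 Visit 3): 8 + 7 = Day 15. A Day 15 Visit 4 is inside the window; Day 16 to 18 is outside.
- Last dose Day 9 (evening before a Day 10 Visit 3): 9 + 7 = Day 16. A Day 15 or 16 Visit 4 is inside; Day 17 or 18 is outside.

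Under the section 7 wording, an AE with in-window onset that is first reported at a Visit 4 held after the window closes would therefore not be treatment-emergent. Under section 8.6.2 it is counted.

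**The case against.** **On worsening.** The strongest reply is that the gap is a data-entry convention. A screening AE pre-exists dosing, section 7 names exacerbation of a pre-existing condition, and section 7.2 requires every AE to be recorded. A site could naturally enter the exacerbation as a new AE with post-dose onset. A condition present before consent is medical history, so its on-drug exacerbation has a post-dose onset anyway. Serious events and AE discontinuations are listed under section 8.6.1 whatever the tables do, and section 4.7.1 sends several important events to discontinuation. All of this narrows the gap to non-serious, non-discontinuing AEs that began in screening. It does not close it, because the duty to record all AEs does not say how to date an AE already recorded.

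**On report date.** Section 8.6.2 is the only place that says what is left out of the tables, and it uses onset. That stands, and it is why this part is only an inconsistency.

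A reader might go further and infer that every AE first reported at Visit 4 would be lost. The documents do not support that. It needs section 7's wording to override section 8.6.2 and the last dose always to fall on Day 7. AEs with onset after the window are also excluded under both rules.

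A reader might likewise take the share of the window left after the End-of-Treatment visit as the size of the problem. With a Day 7 last dose that share is 6/14 = 43% for a Day 8 visit, down to 4/14 = 29% for a Day 10 visit. With the last dose on the evening before Visit 3 it is 6/14, 6/15 or 6/16 (43%, 40%, 37.5%). Either way these are calendar days, not events, and they say nothing about how many AEs are affected.

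**On documents not available.** Section 8 defers detail to an SAP to be finalised before unblinding, and section 7.2.1 refers to a safety reporting plan. Neither text was available for review, and either may address the definition. An SAP can settle which records count. It cannot recover a worsening date that sites never recorded.

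**Conclusion.** The point holds as a minor one. Followed as written, section 8.6.2 drops a non-serious screening AE that worsens on treatment if it stays on its existing record, and no passage in the protocol obliges the site to do otherwise. The opening paragraph of section 7 conflicts with section 7.2, footnote 8 and section 8.6.2, but because section 8.6.2 governs the tables no error in them is shown.

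The documents give no rate for screening AEs, worsening or late reporting, so the number of subjects affected cannot be estimated. It is probably small, given how narrow the remaining group is. Sample size, power and the efficacy analyses are untouched.

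The conclusion assumes that the safety reporting plan does not already tell sites to re-enter a worsened AE. It would be tempting to conclude that the formulation-versus-placebo AE comparison is biased. That would require a drug-attributable excess of lost worsening, for which the documents offer no evidence either way.

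**What to change.** Use one definition in section 7, section 7.2, section 8.6.2 and Schedule footnote 8: a treatment-emergent AE is one with onset from first dose through last dose + 7 days, or a pre-dose AE that increases in severity or becomes serious in that period. This replaces the report-date wording in section 7.

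In section 7.2, instruct sites to record such a worsening as a new AE entry dated from the worsening. The instruction has to reach sites through the protocol or the safety reporting plan while data are being collected; leaving it to the SAP would be too late.

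The cost is about one sentence in each of the four places and one extra recording instruction for sites, with no new visit or assessment. The downside is slightly higher AE counts.
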